10.5.1.2 Sensitivity Analyses of Primary Endpoint

To evaluate the robustness of the analysis results, sensitivity analyses will be performed as follows:

- Non-parametric analyses will be performed
- Multiple imputation for subjects who discontinue IP with missing endpoint data
 - It will be assumed that the missing percent change values will be normally distributed with a mean 0 and a variance-covariance matrix the same as the observed variance-covariance matrix from subjects in the placebo group who did not discontinue IP.
 - If there are at least 25 subjects who discontinue evolocumab but have non-missing week 24 endpoint data, an additional multiple imputation will be carried out utilizing the information from these subjects (mean and variance) to impute the missing data for subjects who discontinue evolocumab and have missing endpoint data

10.5.1.3 Covariate and Subgroup Analyses of Primary Endpoints

As a supportive analysis, the primary analysis will be repeated using the CAS to estimate the on-treatment treatment effect.

In addition to the primary analysis specified in Section 10.5.1.1, covariate-adjusted analyses of the primary efficacy endpoint will be performed as supportive analyses using the baseline covariates in Section 4.2 in their original format, one at a time, in the primary model used in the primary analyses as appropriate.

Statistical Analysis Plan: 20130286

Date: 20 January 2019 **Page 27 of 35**

Subgroup analyses on the primary efficacy endpoint will be conducted using the subgroups specified in Section 7.3. Depending on the distribution of baseline LDL-C, analyses using different subgroups of baseline LDL-C will be performed if applicable. Treatment effect differences among subgroups, which represent subgroup by treatment interactions, will be estimated and tested based on statistics from the subgroup repeated measures models.

For covariate and subgroup analyses, the stratification factors from the eCRF will be used. Differences in stratum assignment between data collection via IVRS and eCRF will be tabulated.

10.5.2 Analyses of Secondary Efficacy Endpoints

The statistical model and testing of the secondary efficacy endpoints (change from baseline and percent change from baseline) will be similar to the primary analysis of the primary endpoint. The secondary endpoints of achievement of target LDL-C < 70 mg/dL at week 24 and LDL-C response of 50% reduction of week 24 LDL-C from baseline will be analyzed using the Cochran-Mantel Haenszel test adjusted by the stratification factors.

Multiplicity adjustment procedures are defined in Section 10.1.

10.5.3 Analyses of Exploratory Endpoints

10.6 Safety Analyses

10.6.1 Adverse Events

The Medical Dictionary for Regulatory Activities (MedDRA) version 19.0 or later will be used to code all events categorized as adverse events (AEs) to a system organ class and a preferred term. Severity of TEAEs will be graded using the CTCAE (Appendix B) and recorded on the Events eCRF. All adverse event tables will be summarized by actual treatment group. Double-blind period TEAEs will be summarized in the primary analysis; open-label period TEAEs will be summarized in the final analysis.

Subject incidence of all TEAEs, serious TEAEs, TEAEs leading to withdrawal of investigational product, and fatal TEAEs will be tabulated by system organ class, high level group term and preferred term in descending order of frequency. Additionally, the

Statistical Analysis Plan: 20130286

Date: 20 January 2019 Page 28 of 35

subject incidence of all treatment-emergent adverse events will be tabulated by system organ class, high level group term and preferred term in descending order of frequency for each baseline statin use stratum.

Summaries of treatment-emergent, serious TEAEs and target IP TEAEs occurring in at least 1% of the subjects by preferred term in any treatment arm will be provided in descending order of frequency.

Subject incidence of treatment-emergent adverse events related to a device will be tabulated by preferred term in descending order of frequency by treatment group.

10.6.2 Laboratory Test Results

Descriptive statistics will be provided for actual values and changes from baseline in select laboratory parameters at each protocol-specified scheduled visit. Laboratory analytes are provided in the protocol Table 3. Lab shift tables using the CTCAE v4.03 or later grading will be used for the select analytes of interest, when applicable.

In addition, CK and liver function test (LFT) abnormalities will be assessed by the incidence overall and by visits of the following categories:

- CK > 5 x ULN
- CK > 10 x ULN
- ALT or AST ≥ 3 x ULN
- ALT or AST ≥ 5 x ULN
- Total bilirubin ≥ 2 x ULN
- (ALT or AST ≥ 3 x ULN) and (Total bilirubin ≥ 2 x ULN and ALP < 2 x ULN)

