4.1.2 Exclusion Criteria

- Subject taking a combination of background lipid-lowering therapy and HIV therapy known to have significant drug-drug interaction as per Table 2
- New York Heart Association III or IV heart failure, or last known left ventricular ejection fraction < 30%
- Known opportunistic infection/AIDS defining illness (including but not limited to candidiasis of bronchi, trachea, esophagus, or lungs, invasive cervical cancer, coccidioidomycosis, cryptococcosis, chronic intestinal (> 1-month duration) cryptosporidiosis, cytomegalovirus disease (particularly cytomegalovirus [CMV] retinitis), HIV-related encephalopathy, herpes simplex: chronic ulcer(s) (> 28 days duration); or bronchitis, pneumonitis, or esophagitis, histoplasmosis, chronic intestinal (> 28 days duration) isosporiasis, Kaposi's sarcoma, lymphoma, mycobacterium avium complex, tuberculosis, pneumocystis carinii pneumonia, recurrent pneumonia, progressive multifocal leukoencephalopathy, salmonella septicemia, toxoplasmosis of brain, or wasting syndrome due to HIV within 1 year prior to randomization
- 204 Myocardial infarction, unstable angina, percutaneous coronary intervention, coronary artery bypass graft or stroke within 3 months prior to randomization
- Type 1 diabetes, new-onset (hemoglobin A1c [HbA1c] ≥ 6.5% or fasting plasma glucose ≥ 126 mg/dL at screening without known diagnosis) or poorly controlled (HbA1c ≥ 10%) type 2 diabetes by central laboratory during screening
- 206 Uncontrolled hypertension defined as sitting systolic blood pressure > 180 mmHg or diastolic blood pressure > 110 mmHg during screening
- Subject has taken a cholesterylester transfer protein inhibitor in the last 12 months prior to randomization
- 208 Moderate to severe renal dysfunction, defined as an estimated glomerular filtration rate < 30 mL/min/1.73 m² during screening

Date: 30 January 2017 Page 21 of 73

209 Persistent active liver disease or hepatic dysfunction defined as Child-Pugh score of C. Stable (in the opinion of the primary investigator and with aspartate aminotransferase [AST] and alanine aminotransferase [ALT] < 5 times ULN and not expected to require new treatment[s] during study) chronic hepatitis C of at least 1 year duration prior to randomization is allowed

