6.3 Hepatotoxicity Stopping and Rechallenge Rules

Permanent Discontinuation

Subjects with abnormal hepatic laboratory values (ie, alkaline phosphatase [ALP], AST, ALT, total bilirubin [TBL]) **and/or international normalized ratio (INR)** and/or signs/symptoms of hepatitis (as described below) may meet the criteria for withholding or permanent discontinuation of Amgen IP or other protocol-required therapies as specified in the Guidance for Industry Drug-Induced Liver Injury (DILI): Premarketing Clinical Evaluation (July 2009).

6.3.1 Criteria for Withholding and/or Permanent Discontinuation of Amgen Investigational Product and Other Protocol-required Therapies Due to Potential Hepatotoxicity

The following stopping and/or withholding rules (Table 1) apply to subjects for whom another cause of their changes in liver biomarkers (TBL, INR and transaminases) has not been identified.

Important alternative causes for elevated AST/ALT and/or TBL values include, but are not limited to:

Hepatobiliary tract disease

Product: Evolocumab

- Viral hepatitis (eg, Hepatitis A/B/C/D/E, Epstein-Barr virus, cytomegalovirus, herpes simplex virus, varicella, toxoplasmosis, and Parvovirus)
- Right-sided heart failure, hypotension or any cause of hypoxia to the liver causing ischemia
- Exposure to hepatotoxic agents/drugs or hepatotoxins, including herbal and dietary supplements, plants, and mushrooms
- Heritable disorders causing impaired glucuronidation (eg, Gilbert's syndrome, Crigler-Najjar syndrome) and drugs that inhibit bilirubin glucuronidation (eg, indinavir, atazanavir)
- Alpha-one antitrypsin deficiency
- Alcoholic hepatitis

Product: Evolocumab
Protocol Number: 20130286
Date: 30 January 2017
Page 27 of 73

- Autoimmune hepatitis
- Wilson's disease and hemochromatosis
- Nonalcoholic fatty liver disease including steatohepatitis
- Nonhepatic causes (eg, rhabdomylosis, hemolysis)

Amgen IP (evolocumab/placebo) and other protocol-required therapies should be discontinued permanently and the subject should be followed according to the recommendations in Appendix A (Additional Safety Assessment Information) for possible DILI.

Rechallenge may be considered if an alternative cause for impaired liver tests (ALT, AST, ALP) and/or elevated TBL, is discovered and the laboratory abnormalities resolve to normal or baseline (Section 6.3.2).

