Appendix A. Additional Safety Assessment Information

Adverse Event Grading Scale

Refer to the NCI Common Terminology Criteria for Adverse Events (CTCAE) Version 4.0. The CTCAE is available at the following link:

http://ctep.cancer.gov/protocolDevelopment/electronic applications/ctc.htm

Drug-induced Liver Injury Reporting & Additional Assessments Reporting

To facilitate appropriate monitoring for signals of DILI, cases of concurrent AST or ALT and TBL according to the criteria specified in Section 6.3 require the following:

- The event is to be reported to Amgen as a serious adverse event within 24 hours of discovery or notification of the event (ie, before additional etiologic investigations have been concluded)
- The appropriate CRF (eg, Event CRF) that captures information necessary to facilitate the evaluation of treatment-emergent liver abnormalities is to be completed and sent to the Amgen.

Other events of hepatotoxicity and potential DILI are to be reported as serious adverse events if they meet the criteria for a serious adverse event defined in Section 9.2.2.2.

Additional Clinical Assessments and Observation

All subjects in whom IP or protocol-required therapies is/are withheld (either permanently or conditionally) due to potential DILI as specified in Sections 6.3.1 and 6.3.2 or are to undergo a period of "close observation" until abnormalities return to normal or to the subject's baseline levels. Assessments that are to be performed during this period include:

- AST, ALT, ALP, and bilirubin (total and direct) is to be repeated within 24 hours
- In cases of TBL > 2x ULN, retesting of liver tests, and bilirubin (total and direct) is to be performed every 24 hours until laboratory abnormalities improve

Product: Evolocumab
Protocol Number: 20130286

Date: 30 January 2017 Page 68 of 73

Testing frequency of the above laboratory tests may decrease if the abnormalities stabilize or the IP or protocol-required therapies has/have been discontinued AND the subject is asymptomatic.

- Initiate investigation of alternative causes for elevated AST or ALT and/or elevated TBL:
 - Obtain complete blood count with differential to assess for eosinophilia
 - Obtain serum total immunoglobulin IgG, Anti-nuclear antibody (ANA), Anti Smooth Muscle Antibody, and Liver Kidney Microsomal antibody 1 (LKM1) to assess for autoimmune hepatitis
 - Obtain serum acetaminophen (paracetamol) levels
 - Obtain a more detailed history of:

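### SAP 10.6.2 does not separate pre-existing from new liver and CK abnormalities, and its only concurrent ALT/AST and bilirubin row adds an ALP limit that the current protocol rule does not have

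*SAP*

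**What the plan says.** **SAP 10.6.2.** The section promises summaries of values and changes from baseline for selected analytes, and shift tables: "Lab shift tables using the CTCAE v4.03 or later grading will be used for the select analytes of interest, when applicable". It then states that "CK and liver function test (LFT) abnormalities will be assessed by the incidence overall and by visits of the following categories". The rows are CK above 5x and above 10x ULN; "ALT or AST ≥ 3 x ULN" and a second row at 5x; "Total bilirubin ≥ 2 x ULN"; and one combined row, ("ALT or AST ≥ 3 x ULN) and (Total bilirubin ≥ 2 x ULN and ALP < 2 x ULN"). No row refers to the subject's baseline.

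**Protocol 4.1.2, criterion 209.** Stable "chronic hepatitis C of at least 1 year duration prior to randomization is allowed", provided AST and ALT are below 5x ULN. Otherwise the hepatic limit is Child-Pugh C. No criterion limits bilirubin as a multiple of ULN.

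**Protocol 6.3.1 and Table 1.** Other explanations for abnormal liver values include viral hepatitis and ("drugs that inhibit bilirubin glucuronidation (eg, indinavir, atazanavir"). The permanent-discontinuation column of Table 1 combines total bilirubin > 2x ULN, or INR > 1.5 off anticoagulants, with AST/ALT > 3x ULN from a baseline below ULN, when no important other cause is present. ALP appears only in the temporary-withholding column.

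**Protocol Appendix A.** It says that "cases of concurrent AST or ALT and TBL according to the criteria specified in Section 6.3 require the following". The first requirement is a serious adverse event report within 24 hours.

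**SAP 1.** The SAP says that it details the analyses of protocol amendment 1, so the current protocol text is the right comparator.

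**The concern.** Two separate things look wrong.

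First, the table is labelled incidence, but it does not ask whether an abnormality is new. Adverse events in this SAP are counted only if they start on or after the first dose (6.3). The liver and CK rows have no matching condition. In a population that may enter with raised transaminases, or with bilirubin raised by HIV drugs, the rows can mix stable background disease with on-treatment change.

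Second, the combined row is the only output that shows transaminase and bilirubin elevation together. Its ALP ceiling makes it narrower, on that condition, than the rule by which the protocol identifies and reports potential DILI. At stake is whether a reader of the study report can match the laboratory table to the reported DILI cases.

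**Working it through.** The plan states no figure that depends on this point, so the check is mainly one of definitions.

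**1. Can an unchanged elevation be counted?** Take a subject with stable hepatitis C and ALT 4x ULN at baseline, week 12 and week 24.
- Entry: 4 < 5, so criterion 209 allows it.
- Visit mapping: SAP Appendix A assigns chemistry from days (1, 126] to week 12 and (126, 210] to week 24. The day 1 sample is outside both windows; the later two are inside.
- Row: 4 ≥ 3, so the subject counts at week 12, at week 24 and overall.
- Change from baseline: 4 − 4 = 0.

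**2. What does this do to a comparison?** Let q be the share of each arm with a persistent pre-treatment elevation, and r the new-onset rate among the rest. The reported incidence is q + (1 − q) × r. Assume, for illustration only, r = 3% on evolocumab and 1% on placebo.

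| q (assumed) | Evolocumab | Placebo | Ratio | Difference |
|---|---|---|---|---|
| 0% | 3.00% | 1.00% | 3.00 | 2.00 points |
| 1% | 3.97% | 1.99% | 1.99 | 1.98 points |
| 2% | 4.94% | 2.98% | 1.66 | 1.96 points |
| 5% | 7.85% | 5.95% | 1.32 | 1.90 points |
| 10% | 12.70% | 10.90% | 1.17 | 1.80 points |

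For q = 2%: 0.02 + 0.98 × 0.03 = 0.0494; 0.02 + 0.98 × 0.01 = 0.0298; 0.0494 / 0.0298 = 1.66. The ratio shrinks towards 1, while the difference falls only by the factor (1 − q).

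**3. The combined row beside the protocol rule.**

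| Condition | SAP combined row | Table 1, permanent discontinuation |
|---|---|---|
| ALT/AST | ≥ 3x ULN | > 3x ULN |
| Baseline ALT/AST | not used | below ULN |
| Bilirubin | ≥ 2x ULN | > 2x ULN, or INR > 1.5 |
| ALP | < 2x ULN | not used |
| Alternative cause | not used | none important |

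Example: baseline ALT 0.8x; on study ALT 4x, bilirubin 2.5x, ALP 2.2x ULN; no alternative cause. Table 1 is met (2.5 > 2, 4 > 3, 0.8 < 1). The SAP row is not (2.2 is not < 2). The subject appears in the ALT/AST ≥ 3x row and in the bilirubin row, but these do not show that both occurred together.

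**4. Is ALP the only reason for such misses?** I compared the two definitions on 384 combinations of ALT, bilirubin, ALP, INR and baseline ALT, assuming no alternative cause. Of these, 48 met the Table 1 conditions: 20 were also in the SAP row and 28 were not. Of the 28, 8 had INR ≤ 1.5, so they met the rule through bilirubin alone, and every one had ALP at or above 2x ULN. The other 20 had INR above 1.5. A further 88 combinations met the SAP row but not Table 1. These counts describe the logic, not expected frequencies.

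**The case against.** **Silence on baseline.** The SAP does not say that it counts pre-treatment values, and its chemistry windows start after day 1. A reader might infer that baseline abnormalities themselves are tabulated as incident; the text does not support that. What stands is that persistent elevations are not separated out. Shift tables help in part, but the analytes are unnamed, each is shown alone, and CTCAE grades need not match these cut-offs.

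**Size.** A reader might infer that pre-existing cases would rival the 1% adverse event rate in the sample size section. Supposing 5–20% hepatitis C, with 5–25% of those at or above 3x ULN, gives 450 × 0.05 × 0.05 = 1.1 to 450 × 0.20 × 0.25 = 22.5 subjects, or 0.25% to 5%. Both prevalences are assumed, the range is 20-fold, and its low end is below 1%. The 1% is also a different quantity: the chance of seeing such an event among 300 evolocumab subjects (1 − 0.99^300 = 0.951). SAP 10.5.1.1 even provides for fewer than 5 subjects in a stratum.

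**Purpose of the rule.** Table 1 governs individual subjects, whereas the SAP table is a descriptive screen, and nothing says that they must coincide. This is fair. Still, the combined row is the only display of concurrence, and the documents do not explain its ALP limit.

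**Cases are not lost.** A reader might infer that DILI cases would vanish from the report. They would not: they are reported as SAEs, serious events and events leading to withdrawal of investigational product are tabulated, and the single-analyte rows still count them. Only the concurrent laboratory count is lost.

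**Importance.** Liver safety might be read as a main reason for the trial. The primary objective is LDL-C and the safety objective is general, so that claim is not available.

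**Conclusion.** The point holds in two limited parts.

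The ALP mismatch is explicit in the current texts. A bilirubin-route case with baseline ALT below ULN, no important alternative cause and ALP ≥ 2x ULN would be an SAE under Appendix A and be absent from the SAP's only concurrent row. How often this would happen cannot be told from the documents.

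The baseline part follows from the absence of any new-onset condition, together with criterion 209. Its effect is dilution and mislabelling. It is not directional bias, because randomization is stratified by hepatitis C and pre-existing elevations should be roughly balanced. Its size depends on a baseline prevalence that the documents do not give, and the table of ratios above is illustration only.

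The efficacy analyses are unaffected, and the safety summaries concerned are descriptive. This is an inexpensive improvement in reporting. No view is taken on which hepatic criteria are clinically right.

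**What to change.** In SAP 10.6.2:

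- Define every CK and liver row as post-baseline.
- Show each row by baseline status, or count it only among subjects below the threshold at baseline with the baseline count beside it.
- Keep the existing combined row and add one beside it: *(ALT or AST ≥ 3 x ULN) and total bilirubin ≥ 2 x ULN, any ALP*.
- Reconcile the SAP categories with protocol 6.3.1 and Appendix A, and state where they differ on purpose.
- Optionally, repeat the liver rows by hepatitis C stratum if numbers allow.

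The added row will not reproduce Table 1: INR, baseline below ULN and alternative cause remain outside it. INR is not in the protocol's routine analyte list (Table 4), so that route would depend on unscheduled results. The row does recover the bilirubin-route cases now lost through ALP.

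The cost is a few extra rows from data already collected and, where incidence is limited to subjects below the threshold at baseline, slightly smaller denominators.

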10.6.3 Vital Signs

Systolic and diastolic blood pressure and heart rate will be summarized for each treatment group using descriptive statistics at each scheduled visit.

10.6.4 Antibody Formation

The incidence and percentages of subjects who develop anti-evolocumab antibodies (binding and if positive, neutralizing) at anytime will be tabulated.

10.6.5 Exposure to Investigational Product

Descriptive statistics will be produced to describe the patient-month exposure to double-blind or open-label investigational product and the categorical representation of dose received.

Exposure definitions are provided in Section 6.3.

Statistical Analysis Plan: 20130286

Date: 20 January 2019 **Page 29 of 35**

10.6.6 Exposure to Other Protocol-specified Treatment

The number and proportion of subjects receiving selected lipid-lowering medications captured on Other Protocol Required Therapy (Lipid Lowering Therapy) eCRF will be summarized by category and preferred term for each treatment group as coded by the World Health Organization Drug (WHODRUG) dictionary. Summaries will be provided for baseline use and use during each study period. The use of antiretroviral therapies captured on the Other Protocol Required Therapy (Antiretroviral Therapy) eCRF will be summarized similarly. In addition, the reasons for a change in Antiretroviral Therapy will be summarized.

11. Changes From Protocol-specified Analyses

Statistical Analysis Plan: 20130286

Date: 20 January 2019 Page 30 of 35

12. Literature Citations / References

Hochberg Y. A sharper Bonferroni procedure for multiple tests of significance. Biometrika 1988;75:800-802.

Wiens BL. A fixed sequence Bonferroni procedure for testing multiple endpoints. Pharmaceut. Statist. 2003; 2:211-215.

The Task Force for the management of dyslipidaemias of the European Society of Cardiology (ESC) and the European Atherosclerosis Society (EAS). ESC/EAS Guidelines for the management of dyslipidaemias. European Heart Journal. 2011; 32:1769–1818.

Product: Evolocumab Statistical Analysis Plan: 20130286 Date: 20 January 2019 Page 31 of 35

13. **Appendices**

Statistical Analysis Plan: 20130286

Date: 20 January 2019 **Page 32 of 35**

Appendix A. Analytical Study week Assignments

Selected endpoints will be summarized by scheduled study visits in descriptive analyses. Since the actual visits may not exactly coincide with their scheduled visit day, the actual visit day is mapped to the study visit generally by non-overlapping consecutive intervals covering the entire time continuum. The mapping intervals for all distinct schedules are summarized in the following table:

	Double-Blind Period			Open-Label Period	
Analytical Study Week	Week 12	Week 20	Week 24	Week 36	Week 52
Scheduled Visit Day	85	141	169	253	365
Vital Signs	(1, 112]	(112, 154]	(154, 210]	(210, 308]	(308, 378]
Body Weight, Waist circumference			(1, 210]		(210, 378]
Fasting Lipids, ApoA1, ApoB, Lp(a), HIV viral load, CD4, Hepatitis C viral load, chemistry, urinalysis, hematology, HbA1c	(1, 126]		(126, 210]	(210, 308]	(308, 371]

Handling multiple records assigned to an analytical study week:

If there is more than one record in a study week interval, the analytical record for that specific study week will be defined as the record closest to the scheduled visit day of that specific study week (7 x study week + 1). If two records are equidistant from the scheduled day, then the earlier record will be chosen. If there are multiple records on the same day, the last record will be used.

Statistical Analysis Plan: 20130286

Date: 20 January 2019 **Page 33 of 35**

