7.2.2 Rescreening

Product: Evolocumab

Subjects who do not meet inclusion criterion 107 are considered screen failures and cannot be rescreened for this study. Suitable subjects who are ineligible at the initial screening for other reasons and have not been randomized can be reconsented and rescreened at a later time, unless they withdraw from screening, provided the study is still enrolling subjects.

For subjects who are rescreened, data from the first screening period will not be used for the analysis. Rescreened subjects who are reconsented will repeat all screening procedures. Rescreened subjects will maintain the originally assigned subject identification number.

7.2.3 **Double-blind Treatment Period**

Visits will occur per the Schedule of Assessments (Table 3) during the double-blind period from day 1 (week 1, baseline) through week 24. Visits during the treatment period must be completed within ± 3 days of the target visit date. For visits with IP administration at the study site, administration should be the last procedure to be performed during each visit.

If a subject withdraws from the study early, all efforts should be made to complete and report the observations as thoroughly as possible up to the date of withdrawal. If possible, the procedures of the week 24 visit should be completed at the time of withdrawal.

7.2.4 **Open-label Period**

Subjects who receive a dose of IP at week 20 will continue in an open-label period. They will receive their first dose of open-label IP at the week 24 visit. Visits will then occur per the Schedule of Assessments (Table 3) at weeks 36 and 52. Visits during the open-label period must be completed within ± 7 days of the target visit date.

End of Study / Safety Follow-up

At week 52 or 30 days after the last administration of IP, whichever is later, a safety follow-up is scheduled to occur. This safety follow-up can be an in-person visit to the study center or another contact with the subject. If the end-of-study visit is < 30 days after the last dose of IP, the subject will be contacted (eg, by phone) at 30 (± 7) days after last IP for safety follow-up.

Product: Evolocumab
Protocol Number: 20130286
Date: 30 January 2017
Page 37 of 73

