6.1 Study Time Points

Enrollment Date

Enrollment Date is the same as randomization date (ie, the date a subject is randomized in the interactive voice response system (IVRS) as recorded on the eCRF).

Statistical Analysis Plan: 20130286

Study Day 1

For each subject, Study Day 1 is defined as the first day of investigational product administration (SC evolocumab 420 mg QM or SC placebo QM). If a subject enrolled but never received IP, Study Day 1 is defined as the enrollment day.

Study Day

For each subject, and for a given date of interest, study day is defined as the number of days since Study Day 1:

Study day = (date of interest – Study Day 1 date) + 1.

If the date of interest is prior to the Study Day 1:

Study day = (date of interest – Study Day 1 date), so that the day prior to Study Day 1 is study day -1.

First Dose Date of SC IP (TR01SDTM)

For each subject, the first dose date of SC IP is defined as the first date of investigational product administration, equivalent to study day 1.

First Dose Date of SC IP in the Open-label period (TR02SDTM)

For each subject, the first dose date of SC IP in the open-label period is defined as the first date of open-label investigational product administration.

Last dose date of Double-blind Investigational Product

For each subject, the last dose date of double-blind investigational product is defined as the date of the last administration of double-blind investigational product.

End of Investigational Product (EOIP) Date

For each subject, the end of investigational product date is defined as the date of decision to end investigational product.

End of Study (EOS) Date

For each subject, the End of Study Date is the date recorded on the End of Study eCRF.

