6.3 Other Study Related Definitions

Analytical Study Week Assignments

Analytical windows will be used to assign parameter measurements to study weeks. The algorithm is provided in Appendix A.

Actual Treatment Group

A subject's actual treatment group is the randomized treatment group, unless the subject receives treatment throughout the double-blind period that is different from the randomized treatment group assignment, in which case the actual treatment group is the treatment received.

Investigational Product (IP)

Double-blind period IP: evolocumab SC 420 mg QM and corresponding SC placebo. Open-label period IP: evolocumab SC 420 mg QM

Double-blind IP Exposure Period in Months

For each subject:

Double-blind IP Exposure Period = [min (TR01EDT

-1, EOIP + 28 days, EOS Date) - Study day 1 + 1]/ 365.25 * 12

Open-label IP Exposure Period in Months

For each subject receiving at least one dose of open-label IP:

Open-label IP Exposure Period = [min (EOIP + 28 days, EOS Date) - TR02SDT + 1]/365.25 * 12

Study Exposure Period in Months

For each randomized subject, Study Exposure Period = (EOS date – Enrollment Date + 1) / 365.25 * 12

Treatment Emergent Adverse Event (TEAE)

Events categorized as Adverse Events (AEs) starting on or after first dose of investigational product as determined by the flag indicating if the adverse event started before the first dose on the Events eCRF and up to and including EOS. Double-blind TEAEs are those that start before the earlier of last dose date of double blind

Statistical Analysis Plan: 20130286

Date: 20 January 2019 Page 16 of 35

IP + 28 days and first dose date of open-label IP. Open-label TEAEs are those that start on or after the date of first dose of open-label IP and start before the earlier of last dose date of open-label IP + 28 days and EOS.

Serious Adverse Event (SAE)

Treatment-emergent adverse events (as defined above) that are indicated as serious on the Events eCRF.

LDL-C Reflexive Approach

For all analyses related to LDL-C, unless specified otherwise, a LDL-C reflexive approach will be used. When calculated LDL-C is less than 40 mg/dL or triglycerides are > 400 mg/dL, the UC LDL-C value from the same blood sample will be used instead, if available.

Achievement of target LDL-C < 70 mg/dL

A subject has achievement of LDL-C < 70 mg/dL if the week 24 LDL-C value is less than 70 mg/dL. If the value is missing, the subject is considered without the achievement.

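### The SAP's week 52 laboratory window closes on day 371, one day before the protocol's visit window ends, while vital signs and body weight from the same visit are accepted to day 378

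*SAP*

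**What the plan says.** SAP Section 6.3 gives the windows general force: "Analytical windows will be used to assign parameter measurements to study weeks. The algorithm is provided in Appendix A". Appendix A then says that "the actual visit day is mapped to the study visit generally by non-overlapping consecutive intervals covering the entire time continuum".

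The Appendix A table has three rows, and each ends with a week 52 interval:

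- Vital signs: (308, 378].
- Body weight and waist circumference: (210, 378].
- Fasting lipids, ApoA1, ApoB, Lp(a), HIV viral load, CD4, hepatitis C viral load, chemistry, urinalysis, hematology and HbA1c: (308, 371].

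The table prints day 365 as the scheduled day for week 52. SAP Section 6.1 counts days so that the first dose falls on day 1: "Study day = (date of interest – Study Day 1 date) + 1".

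For the visit itself, Protocol Section 7.2.4 states: "Visits during the open-label period must be completed within ± 7 days of the target visit date". The schedule of assessments (Protocol Table 3) shows the same 7-day tolerance for the week 52 end-of-study visit. It lists vital signs, body weight and the central laboratory tests all at that visit.

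**The concern.** An analysis window should be at least as wide as the visit window that the protocol gives the sites. Here the laboratory window is one day too short at its upper end. A subject seen on the last permitted day would have blood pressure and weight summarised at week 52, but the lipids, liver tests, CD4 and viral load taken at the same visit would belong to no week. The three rows describe one visit, so ending one of them 7 days before the other two looks like a slip. Nothing in the SAP explains it.

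What is at stake is the completeness of the by-visit end-of-study laboratory summaries. Week 52 is the last laboratory time point of the study, so no later interval exists to catch such samples.

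**Working it through.** **Inputs.** Scheduled-day formula and intervals: SAP Appendix A. Day count: SAP Section 6.1. Visit tolerance: Protocol Section 7.2.4 and Table 3.

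**Step 1: reproduce the plan's own scheduled days.** Scheduled day = 7 × week + 1.

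| Week | 7 × week + 1 | Printed in Appendix A |
|---|---|---|
| 12 | 85 | 85 |
| 20 | 141 | 141 |
| 24 | 169 | 169 |
| 36 | 253 | 253 |
| 52 | 365 | 365 |

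All five agree, so this is the day count that governs the windows.

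**Step 2: protocol window for week 52.** 365 − 7 = 358 and 365 + 7 = 372. That is 372 − 358 + 1 = 15 permitted days.

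**Step 3: compare with the week 52 intervals.**

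| Row | Last day included | Covers day 372? |
|---|---|---|
| Vital signs | 378 | yes |
| Body weight, waist | 378 | yes |
| Lipids and other labs | 371 | no |

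Day 372 is within the protocol window but in no laboratory interval. Days 373 to 378 (6 days) are late under the protocol, yet the other two rows still accept them. The full gap between the rows is 378 − 371 = 7 days.

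**Step 4: size.** One permitted day in 15 is 1/15 = 6.7% of the window. The documents give neither the distribution of visit days nor the number reaching week 52. As an illustration only, suppose that 10% of 450 subjects leave and nobody else does (450 × 0.9 = 405), and that visits are spread evenly over the 15 days. Then 405/15 = 27 subjects would fall on day 372. If visits cluster on the target day, the number would be close to zero. Late visits on days 373 to 378 would add to either figure.

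**Step 5: which analyses are touched.** Under SAP Section 10.1, the open-label results are analysed descriptively on the long-term analysis set. Section 10.6.2 summarises laboratory values by scheduled visit, and CK and liver abnormalities both overall and by visit. The by-visit figures depend on the window. An overall count need not, and the SAP does not say how it treats a sample with no assigned week.

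**The case against.** **The day count.** Protocol Section 7 gives week 4 as an example and labels it study day 28, which is 7 × week. On that label week 52 is 7 × 52 = 364, and 364 + 7 = 371, exactly the laboratory bound. This may be where 371 came from. It does not rescue the bound. The same sentence places the visit 4 calendar weeks after day 1, and 28 days after day 1 is day 29 by the SAP's definition. Appendix A itself uses 365. The label would also not explain why the other two rows end at 378.

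**The effect is slight.** This stands. One permitted day is involved, the summaries are descriptive, and the coverage statement is hedged by the word generally. The SAP nowhere says that out-of-window samples are discarded; that is inferred from the absence of any interval for them.

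**A stronger reading.** A reader might also infer that the week 24 lipid window, (126, 210], is wrong, because it opens before the scheduled week 20 dose (day 141) and 28 days before the vital signs window. Protocol Section 7.2.3 says of subjects who withdraw: "If possible, the procedures of the week 24 visit should be completed at the time of withdrawal". An exit sample from day 127 could thus count as an observed week 24 LDL-C. The subject would then fall outside the sensitivity analysis described as "Multiple imputation for subjects who discontinue IP with missing endpoint data" and outside the responder rule "If the value is missing, the subject is considered without the achievement". The mechanism is real, but the documents do not show an error:

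- In the vital signs and laboratory rows, each cut between visits is the midpoint of the neighbouring scheduled days, minus 1. Vital signs are taken at week 20: (141 + 169)/2 − 1 = 154. Lipids are not, so their neighbours are weeks 12 and 24: (85 + 169)/2 − 1 = 126. The cuts at 112, 210 and 308 follow the same rule: (85 + 141)/2 − 1, (169 + 253)/2 − 1 and (253 + 365)/2 − 1.
- Starting the lipid window after day 154, with week 12 still ending at day 126, would leave days 127 to 154 unassigned.
- It would also set aside LDL-C values that SAP Section 10.5.1.1 says will be used whether or not the subject is still on treatment.
- The direction is not fixed. If an exit value already shows lost effect, removing it leaves the model to predict week 24 from earlier data, which could favour evolocumab.

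**Conclusion.** The week 52 laboratory upper bound is wrong as written. Under the SAP's own day count it excludes day 372, which the protocol permits, and it disagrees with the other two rows for the same visit. The conclusion rests on the 7 × week + 1 convention; it would disappear only under the protocol's day 28 label, which conflicts with the protocol's own calendar-week wording.

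The consequence is minor: 1 of 15 permitted days and up to 6 further days of late visits, with an unknown number of subjects, in descriptive open-label summaries. No hypothesis test, no week 24 result and no trial conclusion depends on it. The width of the week 24 lipid window is a prespecified midpoint choice with arguments on both sides, and this point does not call for a change to it.

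**What to change.** In SAP Appendix A, change the week 52 interval for lipids and other laboratory tests from (308, 371] to (308, 378]. Day 372 is the least that covers the protocol window; 378 also brings the row into line with vital signs and body weight.

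The cost is one number in one table, with no new data and no change to any test. The rule that takes the record nearest the scheduled day still applies, so a later sample is used only when no nearer one exists. One consequence should be accepted knowingly: the scheduled week 48 dose is day 7 × 48 + 1 = 337, so a day 378 sample lies 378 − 337 = 41 days after it, against 365 − 337 = 28 for an on-time visit. Only late visits would be in that position.
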